For Aim 1 (*Nudge* or *Nudge+*), we are requesting waiver of informed consent, so the option to early withdraw from this study is not applicable. For all surveys and interviews administered across aims, the steps to withdraw early from participation will be outlined during the consent process. See the **Consent Process** section below for more details.

5. **Vulnerable Populations:**

We are not targeting any vulnerable populations as part of this study.

6. **Populations vulnerable to undue influence or coercion:**

We will not be targeting participants who are likely to be vulnerable to undue influence or coercion.

STUDY DESIGN:

We will conduct a hybrid type III effectiveness-implementation trial with a longitudinal cluster randomized design to answer questions related to implementation strategy and program effectiveness. We will also apply mixed methods to investigate implementation strategy mechanisms. During the active implementation period, all 41 clinics in the two participating health systems will receive *SAFE Firearm* materials, including brief training in program delivery, cable locks, and the deployment of an EHR implementation strategy. Half of the clinics will be randomized to only receive the EHR implementation strategy (*Nudge*); the other half will be randomized to receive *Nudge* plus 1 year of facilitation to target additional clinician and organizational implementation barriers (*Nudge+*). We will randomize clinics to the active implementation conditions, as cluster randomization is more appropriate for organization-level implementation strategies¹³⁴ and because there is high potential for contamination if we were to randomize at the PCP level.¹³⁵ To ensure balance across conditions, we will use covariate-constrained randomization.¹³⁶ Covariates include health system (HFH, KPCO), clinic characteristics (size of clinic), and clinician characteristics (whether a stakeholder involved in study planning works in the clinic).

Based on historical precedent, we expect minimal staff turnover at the participating clinics during the study. If this does occur, we will follow procedures used in prior clinic-level cluster randomized trials, which involved brief training of new providers as part of their onboarding process at the clinic.

EQUITY SUPPLEMENT STUDY DESIGN:

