- Aim 1 measures will ask questions about PCP fidelity to the two steps of the *SAFE Firearm* program (whichever question was not answered during Part 1; e.g. did your child's PCP talk to you about firearm safety, did your child's PCP offer you a cable lock?). Aim 1 measures may also include questions about acceptability of the *SAFE Firearm* program and parents' reactions to the firearm discussions with providers.
- Aim 3 measures will ask questions about firearm storage behavior (e.g. if they took a cable lock, if all firearms are stored with a gun lock on them, if bullets are stored separate from all firearms, etc.).
- For NIH reporting purposes, we will also collect parent demographics (e.g., gender, race, ethnicity); disclosure of this information will be optional.

- **PCP surveys (Aims 1 and 2).** We anticipate PCP surveys will take about 15 minutes for PCPs to complete. Two surveys will be administered: one will be completed during the 6-month pre-implementation period (baseline survey) and one will be completed during the 1-year active implementation period. Each of the surveys will include questions related to some or all of the following constructs below:
 - Aim 1 measures will ask questions about acceptability and use of the *SAFE Firearm* program and of the implementation strategies. PCPs will also be offered the opportunity to disclose whether they are firearm owners; we will make it clear that disclosure is entirely voluntary.
 - Aim 2 moderator measures will ask questions about PCP attitudes and experiences (e.g., attitudes towards firearm counseling, burnout).
 - Aim 2 mediator measures will also ask about PCP attitudes and experiences (e.g., clinic-level adaptive reserve and PCP motivation to implement *SAFE Firearm*).
 - Demographic questions
- **PCP, Point People, and Leader interviews (Aim 2).** We anticipate interviews with PCPs, point people, and leaders will last about 15-30 minutes. These interviews will be administered once, during the end of active implementation through the early part of the sustainment period. Development of the interview guide was guided by the Consolidated Framework for Implementation Research (CFIR); the guide asks questions about other additional mechanisms through which implementation strategies might operate (e.g. clinician knowledge about firearms, community factors outside the clinic).

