- **Aim 1 Analysis.** Our power analyses are based upon the primary implementation outcome of reach, consistent with best practices for hybrid type III trials.⁶¹ All other implementation outcomes are secondary. Our sample sizes for the project are determined by the fixed number of parent-youth dyads, PCPs, and pediatric clinics within our two health systems. Data are clustered within health system, clinic, and PCP. We expect that approximately 48,475 parents of youth will be eligible to participate each year, and expect to include data from 151 PCPs, within 41 clinics. Therefore, we anticipate obtaining EHR reach data for 48,475 patients during the one-year active implementation period. We base our power calculations on our study design and prior research from our group demonstrating that current PCP use of the *SAFE Firearm* program components are 28% for brief counseling on safe firearm storage and 2% for offering cable locks.¹⁴ We used the PASS power calculation program,⁶² assuming an estimate of an ICC of .07 for explained variance among both PCPs and clinics,⁶³ and conclude that we will have 80% power to detect small effects of the less intensive implementation condition (*Nudge*) on reach (Cohen's d = 0.25 and 0.29, respectively).⁶⁴ Alpha is set at .05 (two-tailed). A small to moderate effect is reasonable to expect based on prior research demonstrating that EHR nudges using active choice approaches produce effects in this range.⁵¹ Because the clinics will be our unit of randomization, it was not necessary to account for the health system ICC in the power analysis. We will account for any differences between health systems by weighting health system the strongest in our covariate constrained randomization. Also, we will conduct a sensitivity analysis that controls for health system as a fixed effect in our analyses and will explore whether intervention effectiveness varies significantly by health system. Our approach is consistent with similar work that has been published in leading medical journals (i.e., Navathe et al., 2019, *JAMA*, Sharma et al., 2019, *JAMA Oncology*). In Aim 1, the primary dependent variable is reach. For each observation period (active implementation, sustainment) and for each implementation condition (*Nudge*, *Nudge+*), we will describe the proportion of clinicians who reported having delivered the program with EHR reach. We will calculate EHR reach using three binary outcomes: received counseling (yes/no), offered lock (yes/no), both (yes/no). We will then conduct separate models. In the first set of models, we will examine whether the odds of receiving components of *SAFE Firearm* increased more in the *Nudge+* group compared with the *Nudge* group between the active implementation and sustainment periods. The fixed effects in the model will include implementation condition (*Nudge*, *Nudge+*), time (active implementation, sustainment), and their interaction; the magnitude and statistical significance of the parameter estimate for the interaction term will be of primary interest. Given the nested data (i.e., parent-youth dyads nested within PCPs; PCPs nested within clinics; clinics nested within health systems), analyses will rely on 3-level logistic mixed effects regression models for reach as a dichotomous implementation outcome.^{65,66} Linear mixed effects regression will be used to model continuous secondary outcomes (e.g., acceptability). For all models, our independent variable of interest will be a binary

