- **Aim 2 Analysis.** *Quantitative analysis.* For our 2-2-1 mediation analyses, we will have approximately 76 PCPs and 20 clinics per study arm. Using the PASS power calculation program,⁶² we anticipate these sample sizes will yield sufficient power to detect a moderate indirect effect (Cohen's $d = .44$) through the clinic-level mediator (i.e., clinic adaptive reserve). We assume there will be a large effect of the strategy on the mediator and of the mediator on the outcome based on previous research.⁶⁸ This is a conservative estimate because the calculation does not account for the additional power that will be gained due to the two measurement time-points for each PCP. We will conduct exploratory analyses to investigate motivation as a mediator. Mediation will be tested using the product of coefficients approach for multilevel mediation analysis,⁶⁹⁻⁷¹ which we have used in previous studies.⁷² In this approach, the total effect of the implementation strategy is parsed into direct and indirect effects associated with the mediator. We will test each mechanism in a separate 2-2-1 mediation model. Path "a" represents the effect of the implementation strategy (*Nudge, Nudge+*) at the clinic level on the clinic-level mediator (i.e., clinic adaptive reserve). Path "b" represents the relationship between the clinic-level mediator (i.e., adaptive reserve) and the three binary reach outcomes (counseling, cable lock, both). We will calculate change in reach for each of the two time-points using the 6 month period preceding each survey administration. An unbiased estimate of the mediated effect is derived via the product of the "a" and "b" paths (i.e., $a \times b$) from these analyses.^{70,71,73} We will test the statistical significance of the mediated effects using the joint significance test.⁷⁴ We will use Monte Carlo simulation methods to derive confidence intervals.⁷⁴⁻⁷⁷ We will repeat this model for our exploratory mediator, motivation. Moderators of the strategies' effects will be tested separately by adding terms for each moderator and its interaction with the implementation strategy to the Aim 1 models only during the active implementation period. These models will estimate the conditional relationships between the implementation strategies and implementation outcomes across different values of the putative moderators. *Qualitative analysis and mixed methods.* Text answers from open-ended questions with parents from Aim 1, and digitally recorded and transcribed interviews with PCPs, point people, and leaders on the mechanisms of the implementation strategies, will be loaded into NVivo qualitative data analysis software. Analysis will be led by the research team guided by an integrated approach,⁷⁸ which outlines a rigorous, systematic method for analyzing qualitative data using an inductive and deductive process of iterative coding to identify recurrent themes, categories, and relationships. We will ensure at least 80% interrater reliability amongst our coders (we will have at least two). The structure of our mixed methods approach is sequential (quantitative data is collected before qualitative data and quantitative data is weighed more strongly than qualitative; QUAN>qual). The function is of complementarity (to elaborate upon the quantitative findings to understand the *how* of implementation), and the process is connecting (having the qualitative data set build upon the quantitative data set).⁷⁹ To integrate the quantitative and qualitative results, we will follow guidelines for best practices in mixed methods⁸⁰ as well as our previous experiences with mixed methods implementation research.⁸¹⁻⁸⁴

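### The Aim 2 mediated effect is called unbiased, but only the strategy is randomised; with no confounding assumption, adjustment or sensitivity analysis stated, a shared clinic trait could be reported as the mechanism

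*Protocol*

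**What the plan says.** The mediation plan is in the Protocol, Statistical Analysis, Aim 2 Analysis. The SAP covers only the primary reach comparison.

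- **Estimator.** "An unbiased estimate of the mediated effect is derived via the product" of the a and b paths. No condition is attached.
- **Test.** "We will test the statistical significance of the mediated effects using the joint significance test". Mediation is declared when both paths are significant.
- **What is randomised.** Under Study Design: "We will randomize clinics to the active implementation conditions". The mediator, clinic adaptive reserve, is not randomised. It is not among the randomisation covariates either; those are health system, clinic size and presence of a planning stakeholder.
- **Outcome in path b.** The three binary reach outcomes. An adjoining sentence says that change in reach will be calculated for each of two time-points from the six months before each survey.
- **Mediator measurement.** Two PCP surveys are planned: "one will be completed during the 6-month pre-implementation period (baseline survey") and the other falls in the active year. The Study Instruments section says that each survey covers some or all of the listed constructs, of which adaptive reserve is one.
- **Covariates.** Under Aim 1, sex and race/ethnicity enter all models. Health system and several youth, PCP and census variables may be considered. Baseline adaptive reserve is in neither list, and Aim 2 gives no list for path a or path b.

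**The concern.** Randomising the strategy makes path a a causal contrast. It does nothing for path b. Clinics with good leadership, stable staffing or slack capacity may score high on adaptive reserve and also document more program delivery. If so, path b is non-zero without any causal effect of adaptive reserve on reach, the product a × b is biased away from zero, and the joint test is biased with it. The word 'unbiased' needs the assumption that there is no unmeasured mediator-outcome confounding, and the protocol does not state it.

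Timing adds a second route. Because reach comes from the six months before each survey, the outcome is recorded before the mediator. Successful delivery could itself raise how staff rate their clinic.

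Adaptive reserve is the primary variable of Aim 2, and the Background calls the mechanism analysis critical to understanding how the strategies work. A stable clinic trait presented as the mechanism would misdirect later use of facilitation.

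**Working it through.** **The plan's own figure.** The protocol sizes Aim 2 on the basis that "we will have approximately 76 PCPs and 20 clinics per study arm" and gives a detectable indirect effect of d = .44. This cannot be reproduced, because neither path size nor the power is given as a number. With 20 clinics per arm the effect detectable on path a at 80% power is 2.802 × √(2/20) = 0.886. Multiplying by 0.5 gives 0.443, but 0.5 for path b is an assumption.

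**Inputs for the check.**
- 30 clinics, 15 per arm (SAP, N=30 cluster means).
- Two-sided 0.05 for each path. The protocol says "Alpha is set at .05 (two-tailed") for Aim 1; it is assumed to apply here.
- Path a of 0.8 SD (assumed; the protocol says large, without a number).
- True path b of zero.
- Within-arm correlation between adaptive reserve and reach, due only to a shared trait, of 0, 0.25 or 0.36 (assumed; no document gives it).

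**Step 1, path a.** Noncentrality = d × √(n/2) = 0.8 × √7.5 = 2.191. The critical t on 28 df is 2.048, so power is 0.562.

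**Step 2, path b with reach as a level.** By Fisher's z, adjusting for arm, the mean of the test statistic is atanh(r) × √(30 − 1 − 3) = atanh(r) × 5.099.
- r = 0.25: 0.2554 × 5.099 = 1.302, probability significant 0.256.
- r = 0.36: 0.3769 × 5.099 = 1.922, probability significant 0.485.

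**Step 3, joint test.** The two tests are close to independent, so multiply:

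| Trait-induced r | Path a | Path b | False mediation |
|---|---|---|---|
| 0 | 0.562 | 0.050 | 0.028 |
| 0.25 | 0.562 | 0.256 | 0.144 |
| 0.36 | 0.562 | 0.485 | 0.273 |

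Clinic-level simulations (5,000 to 8,000 trials per setting) agree: about 3%, 14–15% and 26–29%. With the protocol's 40 clinics the last two rise to about 23% and 43%.

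**Step 4, a second data model.** Here each clinic has about 1,600 visits (48,475 / 30 = 1,616), reach is about 45% (pilot EHR figure in the SAP), and the ICC is 0.07. With 30 clinics, false mediation is about 3% at correlation 0, 19% at 0.3 and 44% at 0.5. The mean of a × b is about 0.12 and 0.20 on the log-odds scale at 0.3 and 0.5, when the truth is zero.

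**Step 5, dependence on path a.** With a = 0 the joint rate at r = 0.36 is about 0.05 × 0.485 = 0.024. With a = 0.4 SD, path a has power of about 0.185, giving 0.185 × 0.256 = 0.047 and 0.185 × 0.485 = 0.090.

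**Step 6, change in reach.** If the outcome is a true pre-to-post change and the trait shifts only the level of reach, the trait cancels. Path b returns to 5% and the joint rate to about 3%.

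**Step 7, baseline adjustment.** If the instrument is equally reliable before and after launch, adding baseline adaptive reserve to both paths leaves about 9–16% at r = 0.25 to 0.36. In the second data model it leaves 9–10% at 0.3 and 20–27% at 0.5. Adjusting for the trait itself brings the rate to 4–5%.

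**The case against.** The strongest reply is the sentence on change in reach. A stable trait that lifts the level of reach would drop out of a true change, and Step 6 shows that false mediation then stays near 3%. This stands as far as it goes, but the protocol does not settle that such a change is what will be modelled. The same paragraph describes path b in terms of three binary outcomes. Aim 1 describes reach only for the active and sustainment periods, and the SmartList is described as on from implementation onward. EHR extraction is planned before launch, but no pre-launch reach is defined. A change score also gives no protection against a trait that affects how fast a clinic improves.

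Second, the test misleads only if the strategy moves adaptive reserve. That is correct. But the protocol assumes a large effect on that path, so it is the planned scenario.

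Third, mixed-methods interviews and an exploratory second mediator also bear on mechanism. They do, and Aim 2 does not stand on this test alone.

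A reader might also infer more than the documents support:
- *That the plan decided against baseline adjustment.* It is silent; two time-points are mentioned only as a source of extra power.
- *That baseline adaptive reserve is certainly available.* The survey description says some or all constructs, so this is likely but not certain.
- *That adding it cures the problem.* Step 7 shows that it does not.

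**Conclusion.** The concern holds. 'Unbiased' does not follow from a design that randomises only the strategy, and neither the Aim 2 text nor the SAP supplies the missing assumption, adjustment set or sensitivity analysis.

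The size is conditional. False mediation of about 14–29%, against about 3% with no shared trait, requires 30 clinics, a real strategy effect of 0.8 SD on adaptive reserve, assumed trait-induced correlations of 0.25 to 0.36, and reach analysed as a level. With no strategy effect on adaptive reserve the joint test keeps its level, and under a well-defined change outcome with a level-only trait it stays near 3%. The correlations are assumptions, so the range shows what is possible and does not predict this trial. Reverse causation from the timing of the reach window is a separate exposure and is not included in these rates.

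This is a point that should be corrected in a mechanism aim. It gives no ground for doubting the primary Nudge+ versus Nudge comparison, which does not use the mediator.

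**What to change.** Change the Aim 2 text of the protocol, or add an Aim 2 section to the SAP, which has none:

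1. Delete 'unbiased'. State that a × b has a causal reading only if there is no unmeasured mediator-outcome confounding.
2. Adjust both paths for baseline clinic adaptive reserve, if the baseline survey carried it, and for health system, clinic size and clinician partner status.
3. Define the reach outcome: level or change, from which months, and how any pre-launch reach is measured. Use a window that starts after the mediator survey.
4. Report how strong a residual mediator-outcome correlation would have to be to remove the indirect effect.

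The cost is wording, a few model terms and one sensitivity analysis. The covariates in item 2 other than adaptive reserve are already in the primary model. The indirect-effect estimate may become smaller and less precise, and a later window may leave fewer active-year visits. Items 1 and 4 are needed even if item 2 is done in full, because baseline adjustment reduces the bias without removing it.

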08 March 2022	Changing primary study outcome from parent-reported receipt of S.A.F.E. Firearm program (i.e., fidelity) to clinician-reported delivery of S.A.F.E. Firearm in the electronic health record (i.e., reach) and other minor protocol revisions ahead of trial launch.	
The protocol was updated in this modification to reflect the change in primary outcome. A detailed description of the rationale for the change in primary study outcome is described below in the Statistical Analysis Plan Summary of changes.
 
Additionally, the protocol was updated in this modification to reflect final decisions and details for the study prior to trial launch:
 
 - Final number of clinics participating in the trial (N = 30) after removal of clinics that no longer met eligibility criteria ahead of trial launch - Covariates included in covariate-constrained randomization of study clinics - Finalized measurement plan and measures to be included in a survey that collected secondary outcomes data from clinicians at participating study clinics 
The Data Safety and Monitoring Board approved of the primary outcome change and the full study protocol on 02 March 2022. The study's National Institute of Mental Health Program Officer also approved of the primary outcome change on 02 March 2022. These approvals were received and this modification to the protocol was submitted (8 March 2022) to the University of Pennsylvania Single Institutional Review Board prior to the trial's launch on 14 March 2022.

22 April 2022	Update protocol details related to administrative supplement award activities and analyses.	This modification pertained to the administrative supplement to the award funding the main trial (R01 MH123491-02S1, PI [name]). The administrative supplement procedures were included in the main trial's IRB protocol. No changes pertaining to the main trial protocol were made as part of this modification.
01 August 2022	Adding Northwestern University as a study site and updating the University of Pennsylvania Site PI listed in the study protocol.	The study's Principal Investigator, [name], left the University of Pennsylvania and transitioned to a new position at Northwestern University on 01 September 2022. Thus, the University of Pennsylvania Site Principal Investigator was updated in the study protocol to study biostatistician [name]. Northwestern University was also added as a relying site, as [name] and her team continued to lead the study from Northwestern University. Finally, the protocol was updated to reflect that [name] team would be (a) recruiting participants for a second survey that collected secondary outcomes data from clinicians at participating study clinics and (b) conducting qualitative interviews with study constituents.
19 October 2022	Updating health system name in study protocol.	One of the participating health systems changed its name; the protocol was updated with this new name.
	Updating data sharing and management details after the PI transitioned to Northwestern University.	Data management protocols were updated to note that study data would be securely shared by the research team at the University of Pennsylvania to the research team at Northwestern University for data management and analysis, consistent with the terms detailed in an updated Data Transfer and Use Agreement that was executed between Northwestern

		University, the University of Pennsylvania, and the two participating health systems.
	Update protocol details related to administrative supplement award activities and analyses.	This modification pertained to the administrative supplement to the award funding the main trial (R01 MH123491-02S1, PI [name]). The administrative supplement procedures were included in the main trial's IRB protocol. No changes pertaining to the main trial protocol were made as part of this modification.
13 December 2022	Updating protocol with finalized plans for qualitative interviews.	
This is the final approved study protocol; no further changes were made for the duration of the trial. The full document is above.
 
Qualitative interviews were conducted with clinicians, clinic change agents, and health system leaders after the active trial year ended. These interviews asked constituents about their experiences of and perspectives on S.A.F.E. Firearm and the implementation strategies, as well as needs for sustaining S.A.F.E. Firearm in the clinics and health systems long-term. The study protocol was updated with the finalized sampling and interview plan in preparation for launching the interviews (which began in May 2023).

Initial approved protocol

Approved by the University of Pennsylvania Single IRB: 08 February 2022

Social and Behavioral Sciences Human Research Protocol**PRINCIPAL INVESTIGATOR:**

[name]

ADDRESS

PHONE; EMAIL ADDRESS

PROTOCOL TITLE: A comparative effectiveness trial of strategies to implement firearm safety promotion as a universal suicide prevention strategy in pediatric primary care

INTRODUCTION AND PURPOSE:

The number of young people dying by suicide continues to rise in the U.S.^{1,2} The risk for suicide death is much greater when there is an unlocked and loaded firearm in the home.³ Two lines of evidence indicate that pediatric primary care is an ideal setting for universal prevention to reduce firearm access and related suicide risk. First, most youth visit primary care each year.⁴ One study found that 77% of youth who died by suicide had accessed primary care in the prior year, with nearly 40% attending a visit within 4 weeks of death.⁵ Second, studies have found that programs deployed in primary care can increase safe firearm storage among parents.⁶⁻⁹ The most rigorous study tested *Safety Check*, found that parents in the intervention group increased safe firearm storage compared to the control group.⁶ These results led the American Academy of Pediatrics¹⁰ and National Academy of Medicine¹¹ to recommend implementation of evidence-based safe firearm storage programs like *Safety Check*, but the core components of the program have yet to become routine clinical practice. Implementation research is urgently needed to realize the potential of this program,¹²⁻¹⁵ especially given that a simulation study found that even a modest increase in safe firearm storage could prevent up to 32% of firearm-related deaths in youth due to both suicide and accidents.¹⁶

The current proposal builds on a previous NIMH-funded project (IRB number 824449) conducted in the Mental Health Research Network (MHRN), in which we interviewed 70 stakeholders, including pediatric clinicians, health system leaders, firearm safety experts, and parents who own firearms. We queried about needed adaptations to *Safety Check*, implementation barriers, and preferred implementation strategies guided by the Consolidated Framework for Implementation Research (CFIR), a leading implementation science framework.¹⁷⁻¹⁹ Adaptation recommendations included renaming the program (now called *SAFE Firearm*), removing the formal screening step and any documentation of firearm ownership in the electronic health record (EHR), and offering brief counseling on safe storage and cable locks to all families.^{17,18} The most frequent implementation strategy suggestion was to integrate the program into the EHR. Studies support the effectiveness and scalability of EHR approaches to make implementation of new practices more salient and part of workflow.²⁰⁻²² Specifically, based on principles of behavioral economics, a well-designed EHR order set can ‘nudge’ clinician behavior.²³ However, our interviews identified implementation barriers that may warrant additional strategies, including clinician comfort with the program and clinic workflow.¹⁹ Facilitation is an evidence-based implementation approach that focuses on building organizational capacity for improvement and directly targets the unique implementation barriers experienced by each clinic.²⁴⁻²⁶ We will answer: Is the less costly and scalable EHR-based ‘nudge’ powerful enough to increase implementation of *SAFE Firearm* or is more intensive and expensive facilitation needed to overcome implementation barriers?

We will conduct a hybrid type III effectiveness-implementation trial with a longitudinal cluster randomized design to answer questions related to implementation strategy and program effectiveness. We will also apply mixed methods to investigate implementation strategy mechanisms. During the active implementation period, all 32 clinics in the two participating health systems will receive *SAFE Firearm* materials, including brief training in program delivery, cable locks, and the deployment of an EHR implementation strategy. Half of the clinics will be randomized to only receive the EHR implementation strategy (*Nudge*); the other half will be randomized to receive *Nudge* plus 1 year of facilitation to target additional clinician and organizational implementation barriers (*Nudge+*). We will collect the primary implementation outcome for 6 months before exposure to condition and for 1 year following to allow for comparisons between (a) the active and pre-implementation periods and (b) the active and sustainment periods. Results will guide future efforts to promote firearm safety as a universal suicide prevention strategy.

EQUITY SUPPLEMENT PURPOSE:

Prior to launching the full trial, we are piloting the delivery of the *SAFE Firearm* program in 2 clinics in each health system during a 1-month period. Pilot procedures will mirror the procedures described in the protocol and use the same parent survey instrument (more details are below). After the pilot, we will conduct this sub-study. Specifically, we will explore any signals of disparities and examine *SAFE Firearm* delivery by children's medical complexity (per ICD-9 and -10 codes) and race/ethnicity. Because we anticipate that clinicians will provide helpful contextualization for the program that will be informative for facilitation for the program and for the broader literature on firearm safety counseling, regardless of whether we detect differences in program delivery, we will interview KPCO and HFHS clinicians who participated in the pilot to identify specific delivery barriers, and convene key stakeholders (e.g., facilitation leaders, pediatric leadership) for virtual meetings. We expect that this step will prime facilitation for trial launch. The goal of this sub-study is to learn more about barriers to delivering the *SAFE Firearm* program equitably to all patients, regardless of medical complexity and race/ethnicity, and to optimize facilitation to address disparities.

An important note about what we are requesting the IRB to review as part of this protocol: Leadership within both health systems has agreed to deploy the Evidence-Based Program (i.e. *SAFE Firearm*) and the Implementation Strategies (i.e. EHR Nudges, Facilitation) within their respective systems. They also are in support of conducting the Research Activities (i.e. quantitative surveys, qualitative interviews, and EHR/Administrative data extraction) to learn more about the implementation of the *SAFE Firearm* program as well as about EHR Nudge and Facilitation strategies. We have described the *SAFE Firearm* program as well as the EHR Nudge and Facilitation strategies in this protocol for reference, but we are requesting IRB review and oversight of only the Research Activities. The *SAFE Firearm* program is evidence-based and the primary research question isn't about effectiveness of this program but rather about implementation. Parents may receive *SAFE Firearm* during a pediatric primary care appointment and not participate in the research survey and vice versa. Requiring consent from participants to receive the *SAFE Firearm* program, EHR Nudge, and/or facilitation would make this implementation research study impossible to conduct because it would create undue bias and be overly burdensome on health systems. The program and strategies are low-risk, evidence-based, and prevention oriented, and ultimately the decision to deliver the *SAFE Firearm* program is left to the individual clinicians for each family. We are looking to answer pragmatic questions about the implementation strategies in a healthcare setting, i.e. is the less costly and scalable EHR-based 'nudge' powerful enough to increase implementation of *SAFE Firearm* or is more intensive and expensive facilitation needed to overcome implementation barriers? The purpose of this study is not to establish *SAFE Firearm* as an effective program, because that has already been done, but rather to study which strategy improves clinician fidelity to the program in a healthcare setting (as reported by parents).

OBJECTIVES:

- Aim 1. Conduct a longitudinal cluster randomized trial to test the comparative effectiveness of two active implementation strategies, *Nudge* (EHR) vs. *Nudge+* (EHR + facilitation).
- Aim 2. To use mixed methods to identify implementation strategy moderators and mediators.
- Aim 3. To examine the effects of *SAFE Firearm* on patient clinical outcomes.

Primary outcome variables:

- Aim 1. Parent-reported PCP fidelity
- Aim 2. Staff-reported clinic adaptive reserve
- Aim 3. Parent-reported firearm storage behavior

Secondary/Other outcome variables (Moderators and mediators to be measured):

- Aim 1. Reach, cable lock distribution, acceptability, cost
- Aim 2.
 - Moderators: Clinic implementation climate and leadership, clinician attitudes to suicide prevention
 - Mediators: Clinician motivation, clinic adaptive reserve
- Aim 3. Youth suicide attempts, deaths, and unintentional firearm injury and mortality

BACKGROUND:

Youth suicide deaths are on the rise in the United States (U.S.). Firearms are a common and lethal method of suicide attempt. Reducing access to lethal means is a promising yet underused suicide prevention strategy.²⁷ Firearms are a critical target of such efforts^{28,29} given that they are present in one in three U.S. homes and these numbers are increasing in the wake of Covid-19.³⁰ Recent research has found that only 3 in 10 firearm-owning families with children store all guns in their home in the safest manner: locked and unloaded. Approximately 4.6 million U.S. children (7%) live in homes in which at least one firearm is stored unlocked and loaded.³¹ Given that the presence of firearms in the home is a robust risk factor for suicide,³² safe storage of firearms in the home is imperative for reducing youth suicide attempts and death. Simulation research has found that even a modest increase in safe firearm storage could prevent as many as 32% of youth firearm deaths due to suicide and accidents.¹⁶ Thus, efforts to increase implementation of interventions to improve safe storage could save young lives nationally.

The success of lethal means safety interventions in other settings highlights their potential value in primary care as a strategy to save young lives. Means safety interventions have been shown to be effective in specialty behavioral health,³³ emergency departments,³⁴ and in the community.³⁵ While these efforts are important, primary care represents a critical opportunity for universal suicide prevention, as it has long served as the de facto mental health services system.³⁶ For example, whereas only one third of youth receive mental health treatment in the year prior to a suicide attempt,^{37,38} four out of five youth who die by suicide visit primary care during that time period.³⁷ Further, at least half of individuals who die by suicide with a firearm have no known psychiatric history,^{39,40} underscoring the importance of universal prevention. With 90% of youth visiting primary care annually⁴¹ and a high rate of primary care visits among youth who die by suicide in the year prior,⁴² primary care provides an excellent opportunity for universal firearm safety intervention.

Safety Check is an evidence-based, pediatric primary care program targeting parental safe firearm storage as part of a bundle of violence prevention strategies.⁶ The program includes screening for firearms in the home, brief counseling around safe storage, and providing cable locks. A large clinical trial in 137 pediatric practices found that parents receiving *Safety Check* reported double the odds of safe storage (OR = 2.0, $p < .011$) compared to the control group. The intervention group showed a 10% increase in use of cable locks, while there was a 12% decrease in safe storage in the control group ($p < .001$). While these results led major professional organizations to recommend implementation of safe firearm storage programs like *Safety Check*, they have not been routinely implemented.¹⁴ There are a number of potential explanations for slow uptake. One potential reason may be the fit of the program for primary care (i.e., program-setting fit).¹⁷ To investigate whether this might be the case and to increase our understanding of how best to implement *Safety Check* as a universal suicide prevention strategy, we conducted pre-implementation work in two health systems, guided by CFIR.¹⁷ This work was particularly salient given that in the 15 years since the *Safety Check* program was designed, there have been advances in implementation science and an increasingly sensitive national debate about firearms, including an evolving role of professional medical associations in advocating for firearm safety as a public health approach. Our preliminary work allowed us to gather key information about barriers and facilitators to the implementation of *Safety Check* in primary care as a universal suicide prevention strategy within the current national context, including primary care provider (PCP) attitudes about discussing firearm safety with parents and firearm stakeholders' attitudes about PCPs raising this topic.^{14,18} Recent work funded through a pilot grant from the FACTS Consortium, an NICHD-funded R24, has allowed us to incorporate stakeholder feedback from this previous work and additional pilot work to adapt *Safety Check* to increase its feasibility and acceptability. This has paved the way for adaptations to the program, now called *SAFE Firearm*, and the development of implementation strategies to be tested in the proposed trial.

